### **3.4 Treatment Period**

#### Part 1

Treatment will start during Visit 1/hour 0 and continue for up to 96 hours.

#### Part 2

MTD treatment will start at Day 1 and continue for up to 14 days.

### **3.5. Study Participation Duration**

Part 1 and Part 2 subjects completing all study assessments will be on study for up to 70 days.

### **3.6 Study Population**

Subjects over the age of 18 with COVID-19 infections and SOB requiring supplemental oxygen to maintain  $\text{SpO}_2 \geq 94\%$  will be enrolled.

## **4. PATIENT SELECTION CRITERIA**

### **4.1. Inclusion Criteria**

1. Signed informed consent from patient or legal representative;
2. Age 18 or greater;
3. Positive reverse transcription polymerase chain reaction (RT-PCR) for SARS-CoV-2 ( $\leq 10$  days of start of infusion);
4. Respiratory rate  $> 20$  RR;
5.  $\text{SpO}_2 < 94\%$  on room air, requiring supplemental oxygen, on mechanical ventilation for  $< 72$  hours (at time of informed consent);

*If screening and infusion occur on the same day, the first  $\text{SpO}_2$  taken at the time of screening needs to be  $< 94\%$  to satisfy eligibility (patient will be put onto oxygen immediately); if screening and infusion occur on separate days, confirm sustained  $\text{SpO}_2 < 94\%$  on room air prior to infusion –if on supplemental oxygen just prior to infusion and  $\text{SpO}_2 < 94\%$  then patient automatically meets the criteria.*

6. Chest X-ray confirming bilateral pulmonary infiltrates;
7. Body mass index of  $\leq 40$  units/kg/m $^2$ ;
8. Adequate method of birth control for subjects of child-bearing potential.\*

*\* Note: A female patient is considered to be of childbearing potential unless she has had a hysterectomy, is at least one year postmenopausal or has undergone tubal ligation. For the purposes of this study, adequate birth control includes at least one medically*

*approved and highly effective method of birth control, defined as those which result in a low failure rate (i.e., < 1% per year) when used consistently and correctly, such as implants, injectables and oral contraceptives combined with the use of double condoms. Only male patients whose vasectomy has been confirmed by semen analysis at least 3 months after the vasectomy are allowed not to use acceptable contraceptive methods.*

#### **4.2. Exclusion Criteria**

1. Terminally ill patients due to underlying cardiac, cancer or severe debilitating neurological disease including coma;
2. Hospitalization expected to be < 96 hours due to medical improvement;
3. Interstitial lung disease;
4. Patients receiving vasopressors at time of starting infusion;
5. Correction of QTc values obtained by 12 lead EKG using Fridericia's formula (QTcF) > 450 ms;
6. History of hypotension (mean arterial blood pressure < 65 mmHg), unrelated to COVID-19 infection;
7. Alanine aminotransferase (ALT) or aspartate aminotransferase (AST) > 3 times upper limit of normal;
8. Creatinine >115umol/L (**Part 2 only**);
9. BUN > 8.3 mmol/L (**Part 2 only**);
10. Participating concurrently on another clinical trial for the experimental treatment of COVID-19;
11. Patients who appear to be showing clinical improvement, in the investigator's opinion (and documented in the source), between screening and baseline (infusion);
12. Active chemotherapy use;
13. Pregnant and/or lactating women.

#### **4.3. Subject Withdrawal**

Subjects may withdraw from the study at any time without stating a reason and without prejudice to further treatment. Incapacitated subjects may be withdrawn by the legally-authorized representative. The reason for withdrawal will be documented in the source notes and in the Electronic Data Capture system (EDC). Any potential or confirmed drug-related event (clinical AE, laboratory abnormality, or other medical condition/situation) occurring, and/or DSMB determination which may be attributed to the withdrawal, must be documented and followed for the safety of the subject.

Withdrawal of a subject from the study applies to subjects who withdraw their consent; otherwise, all subjects will be followed through Day 60. Subjects who are lost to follow-up (attempts to reach subjects will be documented) will be noted as such, at Day 60, but will not be deemed to have been withdrawn; subjects who do not survive to Day 60 will be noted as such but will not be considered to have been withdrawn.

The sponsor should be notified immediately when a subject withdraws consent from the study after any treatment, as every attempt should be made to capture as much information following treatment as possible. If a subject withdraws consent after the start of infusion, for any reason, all attempts will be made to conduct the End of Treatment (Day 5 or Day 16) procedures (See Tables 2 and 3). End of Treatment (Day 5 or Day 16) procedures may be conducted during the 24-hour observation period.

Following discharge, reasonable and diligent attempts to contact the subject should be documented (dates, phone discussions, emails and registered mail) in the subject's record.

#### **4.4. Study Withdrawal Criteria**

The study may be suspended or prematurely terminated at any site if there is sufficient reasonable cause.

Written notification, documenting the reason for the study suspension or termination, will be provided by the suspending or terminating party. If the study is prematurely terminated or suspended, the Investigator(s) will promptly inform the Institutional Review Boards (IRBs) and will provide the reasons for the termination or suspension. The study may resume once concerns about safety, protocol compliance, and data quality are addressed and satisfy the sponsor, IRB, and/or FDA.

Circumstances that may warrant termination include, but are not limited to:

- DSMB determination of unexpected, significant, or unacceptable risk to subjects based on safety evaluations and DLTs;
- Insufficient compliance with protocol requirements;
- Data that are not sufficiently complete and/or evaluable;
- Determination of futility.

### **5. STUDY PROCEDURES AND VISIT SCHEDULE**

#### **5.1. Standard of Care Procedures**

SOC testing obtained prior to consent and within 72 hours of USB002/placebo infusion start can be used to assess eligibility and will not require repeating, unless determined by the Investigator. SOC tests done on hospital admission may be used to determine patient eligibility.

#### **5.2. Clinical Laboratory Evaluations**

Clinical laboratory assessments will be conducted at the local Clinical Laboratory Improvement Amendments certified laboratory routinely used by the Investigator. Laboratory samples will be collected and processed per institution requirements and guidelines.

Laboratory Assessments include:

(Part 1, Screening, Visit 1, 5 and Days 14, 21 and 28)  
(Part 2, Screening, Day 1, Days 7, 16 and 28)

- Chemistry: Sodium, potassium, chloride, carbon dioxide (CO2), calcium, phosphorus, glucose, blood urea nitrogen (BUN), serum creatinine, serum lipase, serum amylase, alkaline phosphatase (ALP), total bilirubin, AST, ALT, lactate dehydrogenase (LDH), LDH isoenzymes, total protein, albumin, triglycerides, uric acid, C-reactive protein (C-RP), creatinine kinase (CK), CK isoenzymes, thyroid stimulating hormone (TSH);
- Hematology: Complete blood count (CBC) to include: Red blood cells (RBC), white blood cells (WBC), complete differential, hemoglobin (Hgb), hematocrit (Hct), mean corpuscular volume (MCV), mean corpuscular hemoglobin (MCH), mean corpuscular hemoglobin concentration (MCHC), and platelet count (Plt);
- Urinalysis: Specific gravity, hydrogen ion concentration (pH), RBC, WBC, protein, and glucose;  
*(Urinalysis for Part 1 only at Screening, Visit 5 and Day 28)*  
*(Urinalysis for Part 2 only at Screening and Day 16)*
- Coagulation: Activated partial thromboplastin time (aPTT), prothrombin time (PT) and international normalized ratio (INR) and fibrinogen assay.

Laboratory Assessments include:

(Part 1: 24, 48, 72 and 96 hours)  
(Part 2: Days 2, 3, 4, 5, 9, 12, 14, 18, 21 and 24)

- Chemistry: Sodium, potassium, chloride, carbon dioxide (CO2), calcium, glucose, blood urea nitrogen (BUN), serum creatinine, alkaline phosphatase (ALP), total bilirubin, AST, ALT, total protein, albumin;
- Hematology: Complete blood count (CBC) to include: Red blood cells (RBC), white blood cells (WBC), complete differential, hemoglobin (Hgb), hematocrit (Hct), mean corpuscular volume (MCV), mean corpuscular hemoglobin (MCH), mean corpuscular hemoglobin concentration (MCHC), and platelet count (Plt);
- Coagulation: Activated partial thromboplastin time (aPTT), prothrombin time (PT) and international normalized ratio (INR) and fibrinogen assay.

### 5.3 Other Assays or Procedures

Other assays or procedures include:

- Pregnancy test (for females of childbearing potential).
- OSCI (Appendix 1);
  - In addition to study required OSCI status collection, any additional OSCI assessments conducted during the study will also be collected.
- SBT (Appendix 2);
- Chest X-ray (required at screening only);

- 12-lead ECG to include HR and QRS intervals, QT/QTcF/QTcB; Correlation of QT values using Fridericia's formula;
- Vitals to be captured daily; and during the infusion period at a minimum of every 8 hours. Vitals to include systolic and diastolic BP, HR, RR and temperature;
  - If BP changes significantly post start of infusion, mean arterial pressure will be collected at 15-minute intervals, until resolution;
- Weight measured at screening only;
- Study-required respiratory assessments (first and last assessments can be based on 24 hour clock or from infusion time):
  - Arterial Blood Gas (ABG): If multiple assessments are conducted daily, the first and last assessment of the day will be collected; missed ABGs do not qualify as deviations,
  - $\text{FiO}_2$  (%) – The highest value in a 24-hour period to be recorded in the event of multiple daily assessments,
  - $\text{PaO}_2/\text{FiO}_2$  ratio, the  $\text{PaO}_2$  value to be obtained from the ABG when performed,
  - Respiratory rate (breaths/min) – The highest value in a 24-hour period to be recorded in the event of multiple daily assessments,
  - $\text{SpO}_2$  (%) – The lowest value in a 24-hour period to be recorded in the event of multiple daily assessments.

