#### 2.1.1 Primary Objectives and Endpoints

The primary objectives of safety and tolerability of USB002 will be evaluated for rate of occurrence and severity of AEs resulting from clinical changes (Visit 1/Day 1 to Day 28): cardiovascular parameters, to include blood pressure (BP), heart rate (HR), 12-lead electrocardiogram (ECG), and requirements for inotropes and vasopressors; laboratory parameters, to include kidney and liver function.

The primary endpoint of preliminary efficacy will be demonstrating the difference between USB002 and placebo groups in time to peripheral capillary oxygen saturation ( $\text{SpO}_2$ )  $\geq 94\%$ , sustained for at least 48 hours, on room air through Day 28.

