##### **Visits 1 – 4 (4, 8, 12, 24, 32, 40, 48, 72 and 96 hours)**

- Blinded Dosing
- Vitals (If no continuous vitals monitoring, collect vital signs per Section 5.3 during the infusion period);
- Respiratory assessments per Section 5.3;

- Laboratory (chemistry, hematology and coagulation per Section 5.2) at approximately 24, 48, 72, 96 hours;
- 12 lead-ECG at approximately 48, 72, 96 hours;
- For mechanically ventilated subjects, SBT at approximately 24, 48, 72, and 96 hours, if weaning criteria met;
- AEs;
- Concomitant medications.

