4.2. Primary Endpoints

The primary endpoint of the study will be safety and tolerability, as demonstrated by adverse events (AE), changes in laboratory assessments, ECG assessments, vital signs, and concomitant medications (inotropes and vasopressors).

The primary endpoint of preliminary efficacy will be demonstrating the difference between USB002 and placebo groups in time to peripheral capillary oxygen saturation (SpO_2) $\geq 94\%$ on room air, sustained for at least 48 hours, through Day 28.

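### Recording the day's lowest SpO2 and highest FiO2 without a shared time leaves the co-primary room-air date imprecise, by up to about one day with daily records

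*Protocol*

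**What the plan says.** Protocol Section 2.1.1 defines the efficacy endpoint as time to SpO2 of at least 94%, "sustained for at least 48 hours, on room air through Day 28". SAP Section 4.2 repeats it ("The primary endpoint of preliminary efficacy will be demonstrating the difference between USB002 and placebo groups in time to peripheral capillary oxygen saturation"), and SAP Section 8.2 calls it co-primary.

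Protocol Section 5.3 governs what is recorded. For SpO2 the entry is "The lowest value in a 24-hour period to be recorded in the event of multiple daily assessments". For FiO2 it is "The highest value in a 24-hour period to be recorded in the event of multiple daily assessments". Each extreme is picked on its own. The section asks for no clock time, no FiO2 or device at the SpO2 reading, and no room-air indicator.

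Several readings a day are part of the design: the Part 1 schedule for Visits 1 to 4 places respiratory assessments at "4, 8, 12, 24, 32, 40, 48, 72 and 96 hours".

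SAP Section 7.2 sets the event time as the date the threshold is first reached on room air, minus the date of first infusion, plus 1. It does not say how room air is established, and it does not carry the 48-hour condition.

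For the PaO2/FiO2 ratio, Section 5.3 names only the numerator: the PaO2 "value to be obtained from the ABG when performed".

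**The concern.** The outcome is a joint condition, but the two retained values can come from different hours of the day. A patient who leaves oxygen in the morning and stays at or above 94% is entered with an FiO2 above room air and a minimum SpO2 whose oxygen state is unknown. That day cannot be counted, although the condition was met for most of it.

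No inference is planned (SAP Section 7.4), so the listed and summarized times are the efficacy result. SAP Section 8.2.6 summarizes them by arm within cohort, and a full cohort has three subjects per arm. At that size, one subject dated 3 days late moves an arm mean by 3/3 = 1 day.

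**Working it through.** The plan gives no figure to reproduce: there is no power calculation, effect size or expected time to event. The steps below size the effect of the recording rule. Readings per day (k), SpO2 paths and FiO2 values are my assumptions. Section 5.3 supports k = 3 only by analogy ("Vitals to be captured daily; and during the infusion period at a minimum of every 8 hours"), because its vitals list does not include SpO2.

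**1. A transition day.** Assume FiO2 0.28 overnight, then room air with SpO2 at or above 94% from 06:00. The condition holds for 18 of 24 hours. The FiO2 entry is 0.28, so the day does not qualify. Conversely, a day whose highest FiO2 is room air and whose lowest SpO2 is at least 94% had no failing reading. The rule can hide a qualifying reading but cannot make a failing day qualify.

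**2. Delay with daily records.** With k equally spaced readings and recovery starting at a random hour, the first qualifying reading is the first of its day with probability 1/k (no delay). Otherwise the date moves to the next day. Mean delay = (k − 1)/k days, which simulation confirmed:

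| k | 1 | 2 | 3 | 6 | 24 |
|---|---|---|---|---|---|
| Mean delay (days) | 0 | 0.50 | 0.67 | 0.83 | 0.96 |

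The maximum is one calendar day.

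**3. Missed runs.** Neither document says how 48 hours is read from daily entries, so take two full qualifying days as the stand-in. Under continuous monitoring, a true run of L hours contains two full days with probability (L − 48)/24, for L from 48 to 72:

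| L (hours) | 48 | 54 | 60 | 66 | 72 |
|---|---|---|---|---|---|
| Probability | 0 | 0.25 | 0.50 | 0.75 | 1 |

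This is the worst case. With k readings a day the outer readings of two days span 48 − 24/k hours, so the probability is (L − 48 + 24/k)/24, capped at 1. At k = 3 that is 8/24 = 0.33 for L = 48, 14/24 = 0.58 for L = 54, and 1 from L = 64. The stand-in would also pass some runs of 40 to 48 hours at k = 3. That slack comes from the stand-in, not from keeping the worst value.

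**4. Part 1 after Visit 5.** The visit lists place respiratory assessments on Days 7, 9, 12, 14 and 16, so the gaps are 2, 3, 2 and 2 days. If Day 9 has several readings and is a transition day, the next scheduled record that can qualify is Day 12, 3 days later. The lists for Days 18 to 28 name no respiratory assessment, so a transition hidden on Day 16 may have no later scheduled record.

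**5. The SAP date.** I simulated rising SpO2 at k = 3, all readings treated as room air (assumed baseline mean 90, between-subject SD 2, rise 0.3 to 0.6 per day, independent reading SD 1 to 3). With two qualifying days required, worst-of-day data gave a date 0.5 to 0.6 day later than the true start of the sustained run. With the SAP rule, which takes the first qualifying day and no 48-hour condition, the mean date ran from 4.7 days earlier to 0.1 day later than that start.

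**6. The comparison between arms.** With assumed exponential mean times of 8 and 12 days and k = 3, recorded means are 8.86 and 12.81 without the rule and 9.54 and 13.49 with it. The differences are 12.81 − 8.86 = 3.95 and 13.49 − 9.54 = 3.95 days.

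**The case against.** Several points on the other side stand.

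- The rule applies only when a day has several assessments. The eCRF and the programming specifications cited in SAP Section 7.2 were not supplied, and nothing says that the scheduled within-day readings are discarded. So it cannot be claimed that only the extremes exist. The gap is that neither document requires a paired, timed reading.
- For a sustained condition, the day's lowest SpO2 is a reasonable conservative measure, since one dip should break the run. This justifies keeping it, but does not supply the oxygen state or the time.
- Infusion stops on the same sustained criterion (Protocol Section 3, Part 2, and synopsis), and SAP Section 8.1.4 lists infusion end times and reasons for incompletion. That is a second route to the date, but in Part 1 only for events completed within the 96-hour infusion.
- The 3-day example owes its size mainly to the visit gap. If Day 9 has a single reading, taken on room air, there is no delay. Even with paired visit readings, 48 hours from Day 9 could not be confirmed before Day 12, although the start would be dated correctly.

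A reader might also infer that PaO2/FiO2 comes out too low. The documents do not support that: Section 5.3 never says the denominator is the day's highest FiO2. If it were, a PaO2 of 80 drawn on 0.40 would give 80/0.60 = 133 instead of 80/0.40 = 200 on a day with a maximum of 0.60. The ratio belongs to no endpoint, and respiratory data are only listed (SAP Section 8.2.2).

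**Conclusion.** The specification gap is real and moderate in size. Data recorded as Section 5.3 directs cannot fix the date on which room-air SpO2 of at least 94% began on any day that mixes oxygen and room air. Taken alone, the rule delays the date by at most one calendar day with daily records, and by up to the 2- or 3-day visit gap where records exist only at visits. It can also miss true runs shorter than 72 hours. These sizes rest on equally spaced readings, random start hours and two full days standing in for 48 hours.

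Two stronger readings are tempting and not supported. The first is that the reported date is late overall: SAP Section 7.2 also drops the 48-hour condition, which pulls the date earlier, so the net direction is undetermined. The second is that the treatment comparison is biased: the same rule applies in both blinded arms, and the worked example leaves the difference unchanged. With three subjects per arm in a cohort the rule can add noise, but that is not bias. With no inference planned and 21 subjects enrolled, all in Part 1 (SAP Section 2), the effect is on descriptive results.

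**What to change.** In Protocol Section 5.3 and on the respiratory eCRF page, record each scheduled SpO2 with its clock time and the FiO2 or oxygen device at that moment, and record the date and time of every change to and from room air. The daily extremes can stay as extra fields.

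In SAP Section 7.2, derive the outcome from paired SpO2 and room-air status, restore the 48-hour condition, and say how 48 hours is established from the available readings.

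For the 21 subjects already enrolled, abstract these items from hospital charts where they exist. Where they do not, state that event dates are accurate only to the recording interval.

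As a minor addition, state that PaO2/FiO2 uses the FiO2 in use when the blood gas was drawn.

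The cost is some extra data entry or, at this stage, retrospective chart abstraction, plus a revised derivation. No new procedure is needed.

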## 5.4 Visit Schedule

### 5.4.1. Screening (Part 1 & Part 2)

The following procedures and assessments must be completed, documented and reviewed by the Investigator within the 72-hour screening period, prior to the first treatment dose (see Tables 2 and 3) unless otherwise indicated:

- Written informed consent, including comprehensive discussion of the study schedule, procedures and protocol requirements with the patient or legal representative;
- Review of demographic data, including date of birth, sex, weight and race;
- Complete medical and surgical history. Any AEs occurring prior to the first USB002/placebo dose will be considered history;
- Medical history to include dates of vaccinations, booster and prior COVID-19 infection(s), if applicable;
- Medical history to include ICU admission date, if applicable;
- Positive RT-PCR for SARS-CoV-2 ( $\leq 10$  days of start of infusion);
- Chest X-ray;
- Comprehensive physical examination (to include lung auscultation to determine presence or absence of lung crackles (rales), wheezing, dullness to percussion);
- 12-lead ECG;

- Sample collection and processing for clinical laboratory assessments (Section 5.2);
- Urinalysis collection (if patient is producing urine) (Section 5.2);
- Vitals assessments (Section 5.3);
- Respiratory assessments (Section 5.3);
- Pregnancy test for females of childbearing potential;
- OSCI;
- Review and documentation of all concomitant prescription and non-prescription medication.

If a randomized subject eligible to proceed to Visit 1 infusion, suffers an AE and/or if the Investigator deems the subject cannot start the infusion, infusion may be delayed up to 72 hours. If the decision to start infusion is > 72 hours, the subject is considered a screen fail and screening procedures must be repeated. In this situation, a new screening number will be used and a new randomization number provided.

#### **5.4.2. Visit Schedule Part 1**

AEs and concomitant medications will be reviewed and documented every day of hospitalization.

##### **Visit 1**

###### *Prior to infusion start:*

- Conduct final determination of eligibility prior to the start of USB002/placebo infusion;
- If not done in previous 72 hours, repeat within 24 hours prior to start of USB002/placebo infusion:
  - Physical exam (for eligibility only, does not need repeating);
  - Laboratory sample collection per Section 5.2;
  - Respiratory assessments per Section 5.3;
  - Vitals;
  - 12 lead-ECG;
  - Chest X-ray (for eligibility only, does not need repeating);
  - Pregnancy test;
  - OSCI assessment.

##### **Visit 1 – 0 hours**

- Infusion start: as soon as possible once deemed eligible.

##### **Visits 1 – 4 (4, 8, 12, 24, 32, 40, 48, 72 and 96 hours)**

- Blinded Dosing
- Vitals (If no continuous vitals monitoring, collect vital signs per Section 5.3 during the infusion period);
- Respiratory assessments per Section 5.3;

- Laboratory (chemistry, hematology and coagulation per Section 5.2) at approximately 24, 48, 72, 96 hours;
- 12 lead-ECG at approximately 48, 72, 96 hours;
- For mechanically ventilated subjects, SBT at approximately 24, 48, 72, and 96 hours, if weaning criteria met;
- AEs;
- Concomitant medications.

